		Page 27, 28, 32, 33, 35 and 37: Changes in wording of IEC requirements	6.6.2.1, 6.6.3, 8.4, 9.1, 9.7.1 and 11.1	REASON: To request approval from IEC only if needed.	
1.2	2015-Nov-02	Page 20 DELETED: The Study Subject Log will allow reconciliation with the subject's hospital files, if needed.	5.5.1	REASON: Hospital files cannot be accessed if informed consent is not obtained from subject.	1.0
		Page 7 DELETED: but some demographic data will be gathered.	Protocol Summary		
1.3	2016-Jul-18	FONT CHANGED: cfb put in italics CHANGED: - GenePOC System changed for → GenePOC System changed for → GenePOC GBS Assay changed for → GenePOC GBS test - GenePOC changed for → GenePOC Inc. - Training manual changed for → Study Site Manual - Specimen changed for → Sample	Whole document	GenePOC nomenclature	1.0
		DELETED: 1.3 Clinical	1 Sponsor	New Information	

Version	Date	Change(s) description	Section	Reason for change (s)	CRF versions to be used
		Research Associate Section. CHANGED: intended use text modified to match the official intended use	Contact		
		ADDED: DTT: Disposable Transfer Tool	Protocol Summary and 3.2 Intended Use	New information	
		CHANGED: - GenePOC System Investigation Documents User's Manual changed for → GenePOC instrument User's manual	2.1 Acronyms	GenePOC nomenclature	
		CHANGED: Disposable Transfer Pipette changed for → Disposable Transfer Tool	2.2 Definitions	To match GenePOC documents nomenclature	
		CHANGED: [...] must repeat the training panel in duplicate and will be qualified if he/she meets the acceptance criteria for each of the repeated runs independently . changed for (a maximum of two times) changed for → [...] must repeat the training panel (a maximum of two times) and will be qualified if he/she meets the acceptance criteria for the repeated runs. changed for (a maximum of two times)	3.3 Device Description	GenePOC nomenclature	
		CHANGED: [...] true negative and high negatives samples. Changed for → and negative sample	5.2.1 Proficiency Testing	Training method updated	
		DELETED GenePOC GBS in the following sentence: Once per day GenePOC GBS , a reference GBS [...].	5.2.4 second paragraph	Not required	
		CHANGED: The operator will save the instrument data on two(2) properly labeled USB keys on each testing day. Once or twice per week, one USB key must be sent to GenPOC. The other USB key must be maintained as a backup at the	5.2.4 Last paragraph	Typo error	
			5.5.2 GenePOC Data and appendix A	New information	

Version	Date	Change(s) description	Section	Reason for change (s)	CRF versions to be used
		Clinical Center. Changed for → The operator will save the instrument data on properly labeled USB keys on each testing day. On every testing day, data will be uploaded to study specific database			
		CHANGED in 2nd bullet:- VWR Multi Tube Vortexer (VWR catalog no. 58816115) and appropriate vial holder; changed for → Tube Vortexer ADDED to 4th bullet: (including PIE, SBT and DTT) DELETED from 8th bullet: isolates DELETED from 10th bullet: Required calibrated pipettes DELETED from 11th bullet: broths and isolates DELETED from 12th bullet: "and shipping to GenePOC once or twice per week" CHANGED in 13th bullet: microfluidic cartridges changed for → PIE	5.6.1 Provided by GenePOC	Administrative changes	
		ADDED to 2nd bullet: GBS collection (if available)	5.6.2 Provided by Investigator	Due to multiple collection sites, GBS sampling procedures may not be available	
		DELETED: The vaginal/rectal swab should be placed into its designed transport media (Amies or Stuart). Care should be taken not to mix stool, water, urine or soap in the sample" ADDED: Vaginal/Rectal swab should be performed in accordance with published guidelines for collection of clinical specimens for culture of Group B Streptococcus (CDC in United States and SOGC in Canada).	6.1 Sample Collection	To reflect what is done in this study using left over sample	
		DELETED: Fresh specimens stored at 2-25°C can be tested with the GenePOC	5.3.1 Inclusion Criteria and	New information	

Version	Date	Change(s) description	Section	Reason for change (s)	CRF versions to be used
		
GBS System and the Reference Method up to 96h of collection.
 
ADDED: If the sample will be processed within 24 hours, store at room temperature. If the sample will be tested after 24 hours, refrigerate until testing is performed. Sample stored at 2-8°C can be tested with the GenePOC GBS System and the Reference Method up to 96h of collection.
	6.2 Sample Storage and Handling, 3rd Bullet		
		
CHANGED: External control materials are not provided by GenePOC. Commercially available control material may be used or a ≥18 hour GBS culture in Lim Broth may be utilized as positive control material. GBS (Streptococcus agalactiae ATCC 12973) is a recommended strain to use as a control. An uninoculated GBS Sample Preparation Reagent tube or a 15 µL aliquot of pure Lim Broth is recommended for use as an external negative control. Preparation of these controls will be detailed in the Package Insert and in the Training Manual. Changed for → External control materials are provided by GenePOC. A reference GBS strain bearing the cfb gene (e.g. ATCC 12973) will be used as a positive external control (EC) while not inoculated Lim broth will be used as a negative EC.
	6.5.1.1 External Controls and 6.5.2 Reference Method	New Information	
		CHANGED: Broth enrichment culture Plate (15 µL) changed for → (100-150 µL)	Appendix B	Typo error	
1.4	2017-Jan-05	CHANGED: [name], B.Sc. for	Whole document	New Study Manager	

Version	Date	Change(s) description	Section	Reason for change (s)	CRF versions to be used
		
[name], M.Sc. and contact information was modified
			
		
DELETED: The GenePOC GBS System and the Reference Method not performed according to the GenePOC GBS Investigation Documents
	Exclusion criteria	This sentence was written twice	
		
ADDED: When it is confirmed that no repeat on fresh Lim broth culture is necessary, it will be transferred to a single appropriately labelled tube and frozen at $-70\pm5^{\circ}\text{C}$ or colder for further testing of all negative frozen samples and /or possible future discrepant testing.
	6.3 Testing algorithm	New Information	
		
ADDED: 6.3.2.3. Repeat of negative samples for the Reference Method
 
In case of suspected irregularity in the testing of the reference method, the entirety of the specimens that gave a negative result with the reference method could be re-tested at a single testing site according to section 6.3.2. In this case, the tested material will be the frozen LIM broth culture stored at -70°C.
	6.3.2 Reference Method	New Information	

PROTOCOL ACCEPTABILITY

Protocol Proposed by:

[name] M.Sc
Study Manager
GenePOC inc.

Date (yyyy-mmm-dd)

Acceptability

I have reviewed and understood this protocol and agree to its provisions. Any modifications must be made by written mutual agreement.

Clinical Center

Address:

Principal Investigator Name

Principal Investigator Signature

Date (yyyy-mmm-dd)

Sponsor

[name], Eng
Director QA/RA
GenePOC Inc.

Date (yyyy-mmm-dd)

PROTOCOL SUMMARY

Study Protocol Number	GenePOC-GBS_clinical-01
Protocol Title	Prospective Multi-Center Study for Clinical Validation of the Molecular-Based GenePOC™ GBS test for the Detection of the cfb gene from Streptococcus agalactiae strains in vaginal/rectal swab sample, after Lim Broth enrichment, from antepartum pregnant women.
System Summary	The primary purpose of this clinical investigation is to verify the performance of the GenePOC GBS test on the GenePOC system. This will be achieved by comparing the GBS test to the Culture, a conventional method for detection of Streptococcus agalactiae in vaginal/rectal swab samples.
Study Locations	Up to four (4) geographically diverse Canadian (2) and US (2) Clinical Centers are targeted, with each site testing high volumes of samples for GBS combined with high prevalence rates and ability to perform the reference method.
Intended Use	The GenePOC GBS test performed on the GenePOC system is a qualitative in vitro diagnostic test designed to detect Group B Streptococcus (GBS) DNA from vaginal/rectal swabs from antepartum women following enrichment in Lim broth for 18-24 hours. The GenePOC GBS test utilizes automated sample preparation and real-time polymerase chain reaction (PCR) to detect a cfb gene sequence specific to the Streptococcus agalactiae genome. The GenePOC GBS test is indicated for the identification of antepartum GBS colonization and does not provide susceptibility results. Culture isolates are needed for performing susceptibility testing as recommended for penicillin-allergic women.
Investigational Product (IUO)	The GenePOC GBS test will be performed according to the Study Protocol using the GenePOC™ instrument. The GenePOC system, used in conjunction with appropriate reagents, is capable of automated cell lysis, dilution of nucleic acids from multiple sample types as well as automated amplification and detection of target nucleic acid sequences.

Reference Method	
Culture is defined as Lim broth culture, subcultured onto blood agar plate (BAP) for observation of a Streptococcus agalactiae strain. More specifically, the Streptococcus agalactiae bacteria, when present, will be isolated using an Enriched Culture and then identified by usual microbiological method.
 
The exact same media type, reagents and procedure will be used for performing the Reference Method throughout the clinical investigation by all sites.

------------------	---

Phase	Development Phase - Qualification of investigational device (IUO).
Planned Study Period	Clinical investigation to begin in January 2016 at the earliest and to be completed within approximately 8 weeks.
Planned Sample Size	The purpose of the clinical investigation is to enroll sufficient samples from four (4) Clinical Centers to obtain a total of 150 samples positive for GBS based on the Reference Method final result. With an estimated prevalence of approximately 25%, up to 600 samples will be tested across all Clinical Centers. The performance obtained and the confidence interval will be monitored during the study in order to stop the enrollment when appropriate. A minimum of 30 positive results per site is expected but sites with a higher prevalence of GBS could contribute with more positive results to reach the required number.
Objectives	
The primary objectives of this multi-center prospective investigational trial are:
 
• To establish the performance characteristics of the GenePOC GBS Assay for its use to detect Group B Streptococcus (GBS) DNA from Lim broth cultures. Sensitivity and specificity will be established in comparison to the Reference Method.• To estimate the Positive and Negative Predictive Values (PPV and NPV) of the GenePOC GBS Assay.• To estimate the rate of unresolved results for the GenePOC GBS Assay due to Sample Processing Control failure (Unresolved sample results).• To estimate the rate of indeterminate results for the GenePOC GBS Assay due to an Instrument failure (Indeterminate sample results).• To determine the reproducibility between sites of the GenePOC GBS System.

Study Design	
Four (4) geographically diverse Clinical Centers will be selected based on a number of criteria, such as investigator and site personnel availability, number of samples of interest tested for Streptococcus agalactiae, GBS prevalence, familiarity with the Study Reference Method, experience with Streptococcus agalactiae culture isolation and clinical studies.
 
Site(s) that will perform the Reference Method will have laboratory facilities where Streptococcus agalactiae characterization methods are performed for routine, investigation or research purposes.
 
This clinical investigation will be composed of the following segments: Proficiency testing, Clinical Accuracy, Discrepant testing (optional) and Assay Reproducibility (selected sites).
 
There are no risks to the patient inherent to the execution of this investigation since it will:
 
1) Be performed on excess de-identified samples only; and2) Include parallel clinical routine testing by an approved and established method for reporting patient results. 
Results obtained from testing using the GenePOC GBS System will be compared to those obtained by the Reference Method. Investigators will ensure that, for a given sample, the participating technicians performing the Assay are masked from the results of the Reference Method and vice-versa.
 
Electronic and/or paper Case Report Form(s) will be used to record pertinent sample and laboratory information. No personal subject information will be collected by GenePOC.
 
In cases of discrepant results between the Reference Method and the GenePOC GBS Assay, GenePOC staff will perform further characterization testing to elucidate the discrepancies.

--------------	--

Clinical Study Main Eligibility Criteria	
• Antepartum pregnant women• 18 years old and more• Gestation period at 35 to 37 weeks• Only one (1) sample per patient will be included in the study.• If the sample will be processed within 24 hours, store at room temperature. If the samples will be tested after 24 hours, refrigerate until testing is performed. Samples stored at 2-8°C can be tested with the GenePOC GBS System and the Reference Method up to 96h of collection.
Clinical Study Statistical Methods	
Results obtained with the GenePOC GBS System will be compared to those obtained with the Reference Method. The statistical analyses will include all compliant samples and will determine at least the following:
 
• The sensitivity and specificity, PPV and NPV as well as exact 95% confidence interval.• The unresolved and indeterminate rates along with 95% exact confidence interval.• Poolability of the data.• Reproducibility percent agreements for qualitative and quantitative data.

TABLE OF CONTENTS

1. INVESTIGATION CONTACTS	15
2. TERMINOLOGY	16
3. INTRODUCTION	18
3.1. Protocol Scope	18
3.2. Intended Use.....	18
3.3. Device Description.....	18
3.4. Test Principle.....	19
3.5. Clinical Benefits and Justification for the Use of a New Technology.....	19
4. TRIAL OBJECTIVES	20
5. STUDY DESIGN	20
5.1. Clinical Investigation Requirements	20
5.2. Overview of the Evaluation	21
5.3. Study Criteria.....	23
5.4. Sample Size Justification.....	24
5.5. Data Collection	24
5.5.1 Case Report Form.....	20
5.6. Study Materials.....	25
6. LABORATORY TESTING PROCEDURES	27
6.1. Sample Collection.....	27
6.2. Sample Storage and Handling.....	27
6.3. Testing Algorithm.....	27
6.4. Storage & Shipping.....	30
6.5. Quality Control Testing	30
6.6. Clinical Trial Quality Assurance	31
7. DATA COLLECTION, MANAGEMENT AND REPORTING	33
7.1. Clinical Center Responsibility.....	33
7.2. GenePOC Responsibility	34
7.3. Data Confidentiality	34
7.4. Data Verification and Validation Rules.....	35
8. CLINICAL TRIAL INCIDENTS, RISK MANAGEMENT AND ADVERSE EVENTS	35
9. REGULATORY AND ADMINISTRATIVE INFORMATION.....	37
10. REFERENCES	41
11. APPENDIX.....	42
11.1. APPENDIX A: Clinical Investigation Requirements Relating to Each Clinical Center	42
11.2. APPENDIX B: Testing Algorithm	44
11.3. APPENDIX C: Discrepant Testing Algorithm	45

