5.2.2. Clinical Accuracy Testing

This clinical study is designed in such a way that all sites may perform the Reference Method, which requires that each Clinical Center has laboratory facilities where GBS characterization methods are performed for routine, investigation or research purposes. Reference method is defined as Lim broth culture, subcultured onto blood agar plate (BAP) for detection of *Streptococcus agalactiae* strains. More specifically, the *Streptococcus agalactiae* bacteria, when present, will be isolated using an Enriched Culture method. The exact same media type, reagents and procedure will be used for performing the Reference Method throughout the clinical investigation by all sites.

To be considered for enrollment in the study, a sample must satisfy all eligibility criteria

described in Section 5.3 of this Protocol. Samples will be collected using a swab.

Sample testing will be performed according to Section 6 of this protocol. Results obtained from testing of samples using the GenePOC GBS System will be compared to those obtained by the Reference Method. These results will serve to verify the GenePOC GBS System performance.

GenePOC GBS System and Reference Method testing will be performed as described in the GenePOC GBS Investigation Documents and the testing algorithm shown in Appendix B. Investigators will ensure that, for a given sample, the PCR operator performing the test are masked from the results of the Reference Method and vice-versa.

The purpose of the clinical investigation is to enroll sufficient samples to obtain approximately 150 positives samples for GBS based on the Reference Method final result. With an estimated prevalence of approximately 25%, it is projected that up to 600 samples will be needed across all participating Clinical Centers.

The Study Manager will monitor sample enrollment and prevalence of GBS across all participating Clinical Centers. It may be necessary to increase the enrollment rate of samples or to prematurely stop enrollment at one or more participating centers, depending upon the total number of samples and the positive samples obtained across all Clinical Centers.

At least three (3) lots of the GenePOC GBS Assay kits will be used for this Clinical trial. Each Clinical Center will test a minimum of two (2) lots.

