5.4. Sample Size Justification

The purpose of the clinical investigation is to enroll sufficient samples from up to four (4) Clinical Centers to obtain a minimum of 150 and a maximum of 160 samples positive for GBS based on the Reference Method final result. With an estimated prevalence of approximately 25%, up to 600 samples could be tested across all Clinical Centers.

A minimum of 30 positive results per site is expected but sites with a higher prevalence of GBS could contribute more positive results to reach the required number. A potential minimum of 200 samples and a potential maximum of 300 total samples will be obtained at each clinical center.

The performance obtained and the statistical confidence intervals will be monitored during the study in order to stop the enrollment when deemed appropriate.

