6.3.1.1. Non-Reportable Results

Samples that initially produce a non-reportable result (Unresolved, indeterminate or External Control failure) will be repeated as described below. Samples that have a reportable (Positive, Negative) result upon repeat testing will be included in the data analyses. Repeated samples that do not give a reportable result will not be included in data analyses. They will be reported separately as non-reportable samples.

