9.7.3. Rules for Discontinuation

GenePOC retains the right to terminate or curtail the study if this study protocol is not followed, or if the device under evaluation requires further development to meet the intended clinical objectives.

The Clinical Center shall terminate the study upon any of the following conditions:

- Completion of the agreed maximum number of positive results or the agreed maximum number of total samples;
- Reaching the date of maximum study duration;
- Withdrawal of approval from the Clinical Center Administration or IEC.

Other reasons and conditions for study termination could be addressed in the Clinical Trial Agreement.

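### The total of up to 600 samples equals 150/0.25, so 150 is the expected number of reference positives at that total and not the minimum that Section 5.4 makes it

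*Combined protocol and SAP*

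**What the plan says.** Three places in the protocol give the size of the accuracy study, in different words.

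- **Protocol Summary, Planned Sample Size.** The aim is "to obtain a total of 150 samples positive for GBS based on the Reference Method final result", and then: "With an estimated prevalence of approximately 25%, up to 600 samples will be tested across all Clinical Centers".
- **Section 5.2.2.** The aim is "to obtain approximately 150 positives samples for GBS", and "it is projected that up to 600 samples will be needed across all participating Clinical Centers". The Study Manager monitors enrolment and prevalence, and may raise the enrolment rate or stop a centre early.
- **Section 5.4.** The aim is "to obtain a minimum of 150 and a maximum of 160 samples positive for GBS based on the Reference Method final result". Up to 600 samples could be tested in all. The same section gives 200 to 300 samples at each centre, with up to four centres.

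Two further sections bear on how enrolment ends. Section 9.7.2 allows the study to be extended if more data are needed. Section 9.7.3 lists the conditions on which a Clinical Center stops, including "Completion of the agreed maximum number of positive results or the agreed maximum number of total samples". It gives no values.

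On what is analysed, the Summary's statistical methods use compliant samples only. Section 5.3.2 excludes samples that lack any required result. Section 6.3.1.1 says of the GenePOC test: "Repeated samples that do not give a reportable result will not be included in data analyses". No expected rate of non-compliance or of non-reportable results is given.

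**The concern.** A sample size found by dividing the target count by the prevalence gives that count on average. It leaves no margin for chance, for a prevalence a little under 25%, or for samples removed before analysis. Section 5.4 nevertheless presents the count as a floor, and states no probability of reaching it.

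The number that is steered is also not the number analysed. Enrolment is directed to positives by the Reference Method final result. Sensitivity is computed only on those that are compliant and have a reportable GenePOC result.

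At stake is the one size the plan commits to for the sensitivity estimate. A reader cannot tell from the documents how many analysable positives to expect, or how many samples will be tested to get them.

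**Working it through.** **Inputs from the documents.** Target 150 positives (Summary, 5.2.2, 5.4), maximum 160 (5.4), prevalence 25%, total 600, 200 to 300 samples per centre, up to four centres. **Assumptions, not in the documents:** the loss rates, the 90% assurance level, independent samples, and losses unrelated to GBS status.

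**1. The plan's own figure.** 150 / 0.25 = 600. It reproduces exactly, so there is no inflation in it.

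**2. If 600 is a ceiling.** Let X be the number of analysable reference positives, X ~ Binomial(600, 0.25 × (1 − d)), with d the share of samples lost.

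| Assumed loss d | P(X < 150) |
|---|---|
| 0% | 0.484 |
| 3% | 0.651 |
| 5% | 0.751 |
| 10% | 0.921 |

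The central 95% range of X is 129 to 171 with no loss and 122 to 163 with 5% loss. With no loss, P(X < 150) depends strongly on prevalence: 0.867 at 23%, 0.703 at 24%, 0.274 at 26% and 0.045 at 28%.

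**3. If 600 is a projection.** Suppose enrolment runs until the 150th reference positive at 25% prevalence. The total needed then follows a negative binomial distribution, with median 599 and 10-90% range 546 to 655. The chance of needing more than 600 equals P(X < 150 at 600 samples) = 0.484. So 600 is the middle of the distribution and not its upper end.

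**4. Total for a 90% chance of at least 150, at 25% prevalence.** The smallest N with P(X ≥ 150) ≥ 0.90 is 655 (no loss), 676 (3%), 690 (5%) and 729 (10%). Inflating for loss alone, 600 / 0.95 = 632, restores only the expected count and leaves the chance of a shortfall near one half.

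**5. The per-centre range.** With four centres, 4 × 200 = 800 and 4 × 300 = 1,200. With three, the range is 600 to 900. At 800 samples and 25% prevalence, P(X < 150) is about 0.001% with no loss and about 0.03% with 5% loss. The two sizes in Section 5.4 therefore have very different consequences.

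**6. Counted against analysed, with no ceiling at all.** If enrolment closes at exactly 150 reference positives, the chance that all 150 are analysable is (1 − d)^150.

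- 0.99^150 = 0.22
- 0.98^150 = 0.05
- 0.95^150 = 0.0005

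At 5% loss the expected number analysed is 150 × 0.95 = 142.5. Closing at 160 would give at least 150 analysable with probability 0.82 at 5% loss, but Section 5.4 does not describe the extra 10 as an allowance for loss.

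**7. Effect on precision.** Exact 95% intervals at an observed sensitivity near 95%:

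| Positives analysed | Detected | 95% interval | Width (points) |
|---|---|---|---|
| 150 | 142 | 89.8% to 97.7% | 7.9 |
| 142 | 135 | 90.1% to 98.0% | 7.9 |
| 122 | 116 | 89.6% to 98.2% | 8.6 |

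**The case against.** The strongest reply is that 600 is not shown to be a hard stop. Section 5.2.2 calls it a projection, Section 5.4 says only that so many could be tested, enrolment is steered by the number of positives, and Section 9.7.2 allows extension. This stands. A reader might infer that the study will miss 150 positives about half the time. The documents do not support that as an unconditional statement: it holds only if 600 is a ceiling and prevalence is 25%. Under the per-centre figures with four centres, a shortfall at 25% prevalence is negligible. The reply does not rescue the wording, however, because a projection exceeded about half the time is not an upper limit, and 800 to 1,200 contradicts 600 within the same section.

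A reader might also take Section 9.7.3 as closing the study at 600. It does not. It is a rule for each Clinical Center, gives no values, and is not tied to 600.

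A third inference would be that any shortfall appears only after enrolment has closed. The plan undercuts this: performance and confidence intervals are monitored during the study (5.4), results are entered within 2 days (7.1.1), and data are validated during as well as after entry (7.4). Most losses could be seen in time to enrol more.

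Finally, it can be argued that the 150 already means compliant samples, since samples must meet the eligibility criteria to be considered for enrolment. The text can be read that way, but each statement of the target names only the Reference Method result, and none requires a reportable GenePOC result. The gap should be closed in words.

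**Conclusion.** The point holds in a conditional form. The 600 is 150/0.25 with no margin, so it makes 150 the expected count and does not support calling 150 a minimum. As a ceiling, it gives a 48% chance of fewer than 150 positives at 25% prevalence, and about 75% if 5% of samples are lost. As a projection, it is exceeded about half the time. Either way the figure needs restating, and it conflicts with 200 to 300 samples per centre when four centres take part.

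The mismatch between positives counted and positives analysed does not depend on whether 600 is a cap. Its size rests on loss rates that the documents do not give.

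The consequence is modest. The documents reviewed state no precision target or performance goal that needs exactly 150 positives, and the sensitivity interval changes by less than one percentage point in width between 150 and 122 positives. This is a correction that should be made to a stated size. It is not a threat to the study's validity.

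**What to change.** In the Protocol Summary, Section 5.2.2 and Section 5.4, in the same words:

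1. Count toward the 150 to 160 only reference positives that are compliant and have a reportable GenePOC result.
2. Say whether 600 is a cap or a projection, and restate the figure in one of two ways. Either 150 is the expected number at 600 samples, with a 95% range of 129 to 171 (about 122 to 163 analysable at an assumed 5% loss). Or 150 is the minimum, and the projected total for a 90% chance of reaching it at 25% prevalence is about 655 (no loss) to 690 (assumed 5% loss). State the loss rate and assurance level used.
3. Reconcile the study total with the 200 to 300 samples per centre and the number of centres.

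The study-wide total should not be written into Section 9.7.3, which applies to each centre separately.

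The cost is wording in three places, and the stated figure becomes less favourable. If the total is raised, there is more laboratory testing but no added patient procedure, because only excess de-identified samples are used (5.3).

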6.3.1.1.2. Indeterminate Result (IND)

For an Indeterminate (IND) result due to an instrument failure, testing of the sample(s) will be repeated from the refrigerated SBT and may be tested with other samples that require repeat testing, or included in a new run with fresh samples. For any IND result, the Study Manager should be contacted and the incident must be documented on the eCRF.

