6.3.1.1.3. External control failure

In case of a failure of either or both external control, the testing of all clinical samples and any repeated samples included in the run will be repeated from the refrigerated SBTs along with new external control (see Section 6.5 for details). In cases where external control fails again, the Study Manager should be contacted.

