8. CLINICAL TRIAL INCIDENTS, RISK MANAGEMENT AND ADVERSE EVENTS

8.1. Clinical Trial Incidents

A Clinical Trial Incident is defined as any problem involving the investigational device, Reference Method, procedures, human subjects, or operators as a result of execution of this Study Protocol. Clinical Trial Incidents may adversely (or potentially adversely) affect human safety, the integrity of the evaluation data, or the operation of devices.

All serious occurrences which affect the health or safety of human subjects or operators involved in this evaluation are considered a Clinical Trial Incident, and may also be determined to be an Adverse Event. Adverse Events are addressed specifically in Section 8.4 below. Since patients are not directly affected by the diagnostic device under evaluation and results are not used for clinical decisions, virtually all Clinical Trial Incidents are not considered Adverse Events.

The Clinical Trials Incident Report Form is used to capture problems or observations arising during the use of the investigational product or in the execution of this Study Protocol and should be reported to the GenePOC Study Manager. The form should be filled out with a full description of the incident, and sent by fax to the GenePOC Study Manager. Incidents might include but are not limited to such occurrences as: instrument failure (IND or other), run incomplete (NA or other), damage or deterioration of the GenePOC GBS System, damage to devices or packaging caused by shipping or

handling, or other incidents deemed to be failures or problems with the product or the execution of this Study Protocol.

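### The sample-level exact 95% interval for the indeterminate rate will be too narrow if an instrument failure affects more than one sample in a run

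*Combined protocol and SAP*

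**What the plan says.** The Protocol Summary lists this among the primary objectives: "To estimate the rate of indeterminate results for the GenePOC GBS Assay due to an Instrument failure (Indeterminate sample results". Section 4 repeats it. The rate is therefore counted in samples, and its cause is the instrument.

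Under Clinical Study Statistical Methods the analysis is introduced by "The statistical analyses will include all compliant samples and will determine at least the following", and the list includes "The unresolved and indeterminate rates along with 95% exact confidence interval". No section names the run or the instrument as a unit of analysis, or plans a clustered or run-level interval.

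On how failures arise:

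- Section 6.3.1.1.2: "For an Indeterminate (IND) result due to an instrument failure, testing of the sample(s) will be repeated from the refrigerated SBT". The optional plural admits one sample or several. The same section lets repeats join a new run with fresh samples, so a run holds more than one sample.
- Section 6.3.1.1.3, on external control failure: "the testing of all clinical samples and any repeated samples included in the run will be repeated". This confirms that runs hold several samples, but the rule covers control failure only.
- Section 8.1 gives as examples of incidents "instrument failure (IND or other), run incomplete (NA or other", so an incomplete run appears as its own item with its own code.

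**The concern.** An exact binomial interval has its nominal coverage only if the counted units fail independently. Clustering within patients is not an issue here ("Only one (1) sample per patient will be included in the study"). The run is the possible cluster, because samples tested together share an instrument and this result is defined by the instrument failing. If one failure can make several samples indeterminate, 600 samples carry less information about instrument reliability than 600 independent trials, and the interval overstates the precision.

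The unresolved rate, listed in the same bullet, is different. Its control is built into each cartridge (Section 6.5.1.2), so it is a cartridge-level event.

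At stake is the stated uncertainty for one of five primary objectives, in data that Section 9.6.1 says will support regulatory submissions.

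**Working it through.** **Inputs from the documents.** Total samples: "With an estimated prevalence of approximately 25%, up to 600 samples will be tested across all Clinical Centers". Check: 150 positives / 0.25 = 600, as stated. The interval is exact 95%, read here as two-sided Clopper-Pearson because sidedness is not stated.

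**Assumptions (not in the documents).** Run size m = 2, 4 or 8. The reproducibility panel in Section 5.2.4 has 8 samples, but that is not given as the instrument's capacity. True indeterminate rate p = 2%. Share f of the risk that strikes whole runs: 0 to 100%.

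**Step 1: one data set, two units.** Take 16 indeterminates in 600 samples (16/600 = 2.67%) and suppose that each failure took out a full run. With design effect 1 + (m − 1)ρ and ρ = 1, the effective sample size is 600/m, which is the number of runs.

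| Unit | Count | Exact 95% interval | Planned upper limit / this upper limit |
|---|---|---|---|
| Samples | 16/600 | 1.53–4.29% | – |
| Runs of 2 | 8/300 | 1.16–5.19% | 4.29/5.19 = 0.83 |
| Runs of 4 | 4/150 | 0.73–6.69% | 4.29/6.69 = 0.64 |
| Runs of 8 | 2/75 | 0.32–9.30% | 4.29/9.30 = 0.46 |

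With weaker correlation the gap shrinks. For m = 8 and ρ = 0.25 the design effect is 1 + 7 × 0.25 = 2.75, the effective sample size is 600/2.75 = 218, and the interval is 0.97–5.78%.

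**Step 2: coverage of the planned interval.** Each of 600/m runs fails as a whole with probability q = f·p. Samples in the other runs fail independently with probability s = 1 − (1 − p)/(1 − q), so the overall rate stays at p. Coverage of the nominal 95% sample-level interval at p = 2% (200,000 simulated trials per cell):

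| Share of risk run-wide | m = 2 | m = 4 | m = 8 |
|---|---|---|---|
| 0% | 96% | 96% | 96% |
| 10% | 95% | 93% | 90% |
| 25% | 93.5% | 88.5% | 82% |
| 50% | 91% | 80% | 64% |
| 100% | 86% | 62% | 59% |

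**Step 3: coverage of possible remedies.** In the same scenarios, an exact interval on runs with at least one indeterminate covers the run-level rate at least 95% of the time in every cell.

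The clustered intervals for the sample-level rate are less reliable. With m = 8 and 50 to 100% of the risk run-wide, an exact interval on an estimated effective sample size covers about 76–80%, and a percentile bootstrap over runs about 72–77%. One reason is that, with 75 runs and all failures run-wide, no run fails with probability 0.98^75 = 22%. The bootstrap then returns 0–0%, whereas the exact interval on 0/75 runs has an upper limit of 1 − 0.025^(1/75) = 4.8%.

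**The case against.** The strongest objection is that clustering is not shown. A reader might infer that a failed run makes all its samples indeterminate, so that the planned interval is simply wrong. The documents do not say this:

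- The optional plural in Section 6.3.1.1.2 is satisfied by a single sample.
- The rule that a whole run is repeated belongs to external control failure (Sections 5.2.2, 5.2.4 and 6.3.1.1.3). The contrast in wording with the indeterminate rule points, if anything, the other way.
- Section 8.1 codes an incomplete run as NA or other, apart from the indeterminate instrument failure. Two aborted runs of 8 might therefore add nothing to the indeterminate count.
- The Package Insert and User's Manual, which may settle the point, are not among the documents supplied.

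This objection stands in full against an unconditional claim. A second tempting reading, that the reported upper limit would be less than half of what the data support, also fails as a general statement. Within runs of 2 to 8 it needs runs near 8 and nearly all failures run-wide.

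Two further objections stand in part. The objective is descriptive, with no acceptance limit or precision target for this rate, so no decision rule is breached. Section 6.3.1.1.2 already requires each indeterminate to be documented, and the list of analyses is a minimum, so a run-level count could be added without contradicting the plan. Both lower the urgency. Neither supplies a planned interval that remains valid if failures are shared within a run.

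**Conclusion.** The point holds conditionally. The planned interval is sound if instrument failures are confined to single samples, and too narrow if they affect several samples in a run. The documents leave open which is the case.

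Under assumed runs of 2 to 8 and a 2% rate, coverage goes from about 96% (independent failures) through about 90% (runs of 8, 10% of the risk run-wide) to about 59% (runs of 8, all run-wide). With runs of 2 and 10% run-wide, nothing is lost. For 16/600, the upper limit of 4.3% on samples compares with 5.2%, 6.7% and 9.3% on runs of 2, 4 and 8 if every failure is run-wide. All of these figures rest on the assumed run size, rate and run-wide share.

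Sensitivity, specificity and the predictive values are not touched, nor is the target of 600, which follows from the number of positives.

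**What to change.** Add to the statistical methods:

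1. Keep the sample-level indeterminate rate as the point estimate.
2. As the reliability measure, report the number of runs with at least one instrument-failure indeterminate out of runs started, with an exact 95% interval. This is a different quantity from the sample-level rate and should be labelled as such. It still assumes that runs fail independently of one another.
3. If any run has more than one indeterminate, also give the sample-level rate a run-clustered interval. State that it is approximate when few runs fail and that a bootstrap over runs cannot be used when none does.
4. State whether incomplete (NA) runs count as indeterminate.
5. Leave the unresolved rate with its exact interval.

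The cost is a few sentences and a little more analysis. Instrument data are already saved each testing day (Section 5.5.2) and daily runs exported (Appendix A), so no new data collection is needed. The downside for the sponsor is a wider, less favourable interval if failures do cluster. If every failure proves to be confined to one sample, the planned sample-level interval stays as it is.
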